4.3.3 Investigational Medicinal Product Accountability

Part 1 (OLE)

All investigational medicinal products (IMPs) required for completion of this study, namely, etrolizumab, will be provided by the Sponsor. The investigator is responsible for the control of the drugs under investigation. The investigational site will acknowledge receipt of IMP (e.g., drug receipt record) and disposition (e.g., drug dispensing log). Accountability will be assessed by maintaining adequate drug dispensing and return

records. Interactive voice/Web-based response system (IxRS) will be used to confirm the shipment condition and content. Any damaged shipments will be replaced.

Accurate records must be kept for all study drug provided by the Sponsor.

These records must contain the following:

- Documentation of drug shipments received from the Sponsor (date received and quantity)
- Disposition of unused study drug not dispensed to patients
- Drug Dispensing Log must be kept current and should contain the following information:

Identification of the patient to whom the study medication was dispensed

Date(s) and quantity of the study medication dispensed to the patient

Date(s) and quantity of the unused study medication returned by the patient

All records and drug supplies must be available for inspection by the study monitor.

4.3.3.1 Assessment of Compliance Part 1 (OLE)

Patient compliance will be assessed by maintaining adequate drug dispensing logs, the patient e-diary, and return records.

Home injection: An e-diary will be provided to patients to record home injections. Patients will be asked to return all unused PFS in the provided boxes at each visit as a measure of drug accountability and patient compliance. Site personnel will monitor the medication records from the e-diary via an online portal. However, patients should bring the e-diary to the clinic during each visit.

Sharps containers for any used PFS will be provided to patients for home usage. After home injections, the used syringes must be placed into the sharps containers immediately. The sharps containers should be returned to sites. Sharps containers will be discarded by the site staff at the frequency per local schedule.

A Drug Dispensing Log must be kept as described in Section 4.3.3. The investigator is responsible for ensuring that dosing is administered in compliance with the protocol. Delegation of this task must be clearly documented and approved by the investigator. When the study is completed, the investigator will return all completed Drug Dispensing Logs to the Monitors.

Any unused study drug and Drug Return Records should be returned to the Monitor, unless alternate destruction has been authorized by Roche or required by local or institutional regulations (Section 4.3.3.2). The investigator's copy of the Drug Return Record(s) must accurately document the return of all study drug supplies to Sponsor.

4.3.3.2 Destruction of the Investigational Medicinal Product Part 1 (OLE)

Any used PFS will be placed into the sharps containers immediately after SC injections either at site or at home. The sharps containers should be discarded at the study site by the site staff per local schedule. Written documentation of destruction of unused study drug must contain the following:

- Identity (batch numbers or subject numbers) of IMP(s) destroyed
- Quantity of IMP(s) destroyed
- Date of destruction
- Method of destruction
- Name and signature of responsible person who destroyed investigational product(s)

In case of device failure or if there are any issues with the drug, the PFS should not be destroyed, and instead should be returned to the study site in the packaging provided for this purpose. The device is to be sent from the investigator site to the appropriate Roche Clinical Trial Supplies Department for further assessment (see Section 4.3.3.3).

4.3.3.3 Reporting of Prefilled Syringe Complaints/Events Part 1 (OLE)

The investigator should report all medical device complaints to the Sponsor. The investigator must document as much information as possible on the PD103 IMP deviation form, including product batch number and expiration date, and forward the complaint form to the Sponsor within 24 hours of the investigator becoming aware of the event. PD103 IMP deviation form, together with pictures of the defective PFS, should be sent to [contact].

Where possible, the investigator will retrieve the PFS unit(s) involved in the complaint and attempt to return it to the Sponsor for further assessment.

If the medical device complaint results in an adverse event, an Adverse Event eCRF must be completed and submitted through the electronic data capture (EDC) system immediately (i.e., no more than 24 hours after learning of the event). If the event is serious, the Adverse Event eCRF must be completed and submitted through the EDC immediately (i.e., no more than 24 hours after learning of the event), as outlined in Section 5.4.1. If the medical device complaint results in an adverse event to an individual other than the study patient (*e.g. nurse at the site or relative/caregiver during a home administration*), the device complaint must be reported on the PD103 IMP deviation form. The adverse event must be reported to the Sponsor as a spontaneous adverse event (*see Section 5.4.6*).

4.4 STUDY ASSESSMENTS

The schedules of assessments are provided in the Study Flowcharts in [Appendix 1](#), [Appendix 2](#), and [Appendix 3](#). Study assessments are detailed below and will be undertaken at study visits as indicated in the Schedule of Assessments. Assessments will be performed only after informed consent has been obtained.

4.4.1 Description of Study Assessments in Part 1 (OLE)

On the final visit of the Phase II OLE or Phase III controlled study, patients should have had procedures and laboratory assessments performed as part of their withdrawal visit. Therefore, to minimize burden on the patient, results from the single set of procedures and laboratory assessments from the final visit of the Phase II OLE or Phase III controlled study will be used for analysis and data sets for the first visit of the OLE-SM study, with the exception of ATA samples, which must be collected at Week 0 if the Week 0 visit occurs >7 days after the final visit of the Phase II OLE or Phase III controlled study. Only if any procedure and assessment was missed at the time of the final visit, it should be performed for the first visit of the OLE-SM study.

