4.1.1 Inclusion Criteria

Part 1 (OLE)

- Patients who were previously enrolled in the Phase II OLE study or a Phase III controlled study and meet the eligibility criteria for treatment with open-label etrolizumab as described in [Table 1](#) (see Section [3.1.1.1](#)) may enroll in Part 1 (OLE) of the study. These patients must provide written informed consent and comply with the requirements of the OLE-SM protocol.

Patients not in safety follow-up or PML follow-up within Study GA27927 and whose last dose of etrolizumab is by July 2016 may enroll in Part 1 (OLE) of Study GA28951, if eligible, and receive their first dose in this study 4 weeks after their last dose in Study GA27927. On occasions where this first dose of etrolizumab cannot be administered in accordance with these requirements, the first dose of etrolizumab is to be administered with a maximum delay of 2 weeks (i.e., up to 6 weeks after their last dose of etrolizumab in Study GA27927).

Eligible patients who exit from Study GA28948 or GA28949 at Week 10 because either they did not achieve clinical remission or they required the use of rescue medication prior to the Week 10 timepoint should not receive their first dose of open-label etrolizumab in Study GA28951 until 2 weeks after the Week 10 timepoint in the Phase III controlled study to allow for adalimumab washout. The first dose of etrolizumab given to these patients entering Study GA28951 should not exceed 4 weeks following the Week 10 timepoint from the Phase III controlled study.

With the exception of VHP countries participating in GA28949 and Estonia (participating in GA28948): Patients who remain in Study GA28948 or Study GA28949 through Week 14 because they have achieved clinical remission may enroll in Part 1 (OLE) of Study GA28951 at Week 14. The first dose of open-label etrolizumab will be given on Day 1 upon enrollment into Part 1 (OLE) of Study GA28951. The first dose of etrolizumab given to the patients entering

Study GA28951 should not exceed 2 weeks following the Week 14 timepoint from the Phase III controlled study.

With the exception of VHP countries participating in GA28949 and Estonia (participating in GA28948): Eligible patients who receive rescue medication between Weeks 10 and 14 may enroll in Part 1 (OLE) of Study GA28951 at Week 14.

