4.1.2 Exclusion Criteria

Part 1 (OLE)

- Withdrawal of consent from the Phase II OLE study or any of the Phase III studies
- Patients who discontinued etrolizumab/etrolizumab placebo prior to Week 10 or did not perform the Week 10 visit of the Phase III Studies GA28948, GA28949, GA29102, and GA29103
- Patients who discontinued etrolizumab/etrolizumab placebo prior to Week 14 or did not perform the Week 14 visit of the Phase III Study GA28950
- Inability to comply with the study protocol, in the opinion of the investigator
- Patients not compliant in the Phase II OLE or Phase III studies or did not complete the required washout period for an active comparator in Studies GA28948, GA28949, and GA29103
- Pregnancy or lactation

Exclusion Due to Safety Reasons

- Patients who developed an anaphylactic/anaphylactoid or severe allergic reaction to study medication during the Phase II OLE or Phase III studies
- Patients who experienced or have an ongoing serious infection event (except for those listed below) should not receive study drug until the event has completely resolved and treatment with anti-infective medications has been completed
- Patients who experienced a specific de novo or reactivated serious viral infection such as hepatitis B virus (HBV), hepatitis C virus (HCV), or HIV during the Phase II OLE or Phase III studies
- Patients who develop cytomegalovirus (CMV) colitis leading to early treatment discontinuation in the Phase II OLE or Phase III studies
- Patients who develop life-threatening infections during the Phase II OLE or Phase III studies

- Patients who developed a malignancy (with the exception of local and resected basal or squamous cell carcinoma of the skin), or who develop adenocarcinoma in situ (AIS), high-grade squamous intraepithelial lesions (HSIL), or cervical intraepithelial neoplasia (CIN) of Grade > 1 on cervical Pap smear, or who develop colonic dysplasia during the Phase II OLE or Phase III studies
- Receipt of the following since commencement of the Phase II OLE or Phase III controlled studies:
 - Any investigational treatment, including investigational vaccines
 - Use of agents that deplete B or T cells (e.g., alemtuzumab or visilizumab), except AZA and 6-MP
 - Use of anti-adhesion molecules
 - Use of JAK inhibitors*
 - Use of cyclosporine, tacrolimus, sirolimus, or mycophenolate mofetil (MMF)
 - Patients who have previously received rituximab, natalizumab, vedolizumab, or efalizumab may not enter the study

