4.4.1.4 Laboratory Assessments

Laboratory assessments will be performed as indicated on the Schedule of Assessments (see the Study Flowchart in [Appendix 1](#) and [Appendix 2](#)). With the exception of urine pregnancy tests, all laboratory investigations will be performed by a central laboratory. Urine pregnancy tests will be performed at specified subsequent visits or in the patient's home. If a urine pregnancy test result is positive, it must be confirmed by a serum pregnancy test.

On days of etrolizumab administration, indicated laboratory samples should be drawn prior to study drug administration. Laboratory assessments will include the following:

- Hematology (hemoglobin, hematocrit, platelet count, RBC count, WBC count, absolute count [neutrophils, eosinophils, lymphocytes, monocytes, basophils, other cells], mean corpuscular volume, mean corpuscular hemoglobin, mean corpuscular hemoglobin concentration, and red cell distribution width)
- Serum chemistries, including liver function tests (sodium, potassium, chloride, bicarbonate, glucose, blood urea nitrogen, creatinine, calcium, phosphorus, magnesium, total and direct bilirubin, total protein, albumin, alanine aminotransferase, aspartate aminotransferase, lactate dehydrogenase, alkaline phosphatase, creatine phosphokinase, and uric acid)
- C-reactive protein (CRP)
- Pregnancy test: All women of childbearing potential (including those who have had a tubal ligation) will have a urine pregnancy test performed at monthly intervals. Pregnancy tests are to be conducted at home on a monthly basis when drug administration is in the home setting and the outcome of the pregnancy test should be recorded on an e-diary. If a urine pregnancy test result is positive, it must be confirmed by a serum pregnancy test.

- Serum samples will be collected for the detection and characterization of ATAs. ATA samples will be analyzed using validated assays. ATA samples may also be utilized for exploratory PD biomarker assessments or assessment of etrolizumab concentrations.
- Serum samples will be collected for monitoring the etrolizumab concentration (PK) during the long-term dosing period. PK samples will be analyzed using validated assays.

Unless the patient gives specific consent for his or her leftover samples to be stored for optional exploratory research (see Section 4.4.1.7), biological samples will be destroyed when the final Clinical Study Report has been completed, with the following exceptions:

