Appendix 1 Open-Label Extension (Part 1, OLE) Schedule of Assessments (cont.)

Part 1 (OLE)	In-Clinic Etrolizumab Administration Every 4 Weeks				At-Home Etrolizumab Administration Every 4 Weeks (or in clinic administration if unable to perform at home)				
	Clinic Visit at Every 4 Weeks, Starting at Day 1 of Week 0 (± 3 days)				Clinic Visit at Every 12 Weeks, Starting at Day 1 of Week 0 (± 3 days)	Clinic Visit at Every 48 Weeks, Starting at Day 1 of Week 0 (± 7 days)	Clinic Visit at Week 108 (-14 days)	Unscheduled Visit ^c	Early Withdrawal from Treatment Visit ^d
	0 ^{a, b}	4	8	12					
Flexible sigmoidoscopy (or colonoscopy, IF REQUIRED) with colonic biopsies ^k							x ^l		x ^j
Pregnancy test ^m	x	x	x	x	x	x	x		x
Hematology ⁿ	x			x	x	x	x	x ^c	x ^h
Chemistry ^o	x			x	x	x	x	x ^c	x ^h
Hepatitis B DNA ^p	x			x	x	x	x		
Serum (CRP)	x					x		x ^c	x ^h
Etrolizumab administration	x	x	x	x	x	x	x		
Etrolizumab PK sample (serum) ^q	x			x		x	x		
Anti-therapeutic antibody sample (serum) ^q	x			x		x	x	x ^c	x ^h

ATA= anti-therapeutic antibody; BP = blood pressure; CRP = C-reactive protein; ECG = electrocardiogram; eCRF = electronic case report form; GI = gastrointestinal; LFT = liver function test; PK = pharmacokinetic; PML = progressive multifocal leukoencephalopathy.

Note: All assessments and blood draws are to be conducted prior study medication administration. All visit intervals based on Day 1 of Week 0.

^a Day 1 of Week 0.

^b Week 0 procedures and laboratory assessments that have been collected as part of the final visit for the Phase II OLE and Phase III controlled studies do not need to be repeated, with the exception of ATAs, which must be collected at Week 0 if the Week 0 visit occurs >7 days after the final visit of the Phase II OLE or Phase III controlled study.

Appendix 1

Open-Label Extension (Part 1, OLE) Schedule of Assessments (cont.)

- ^c Unscheduled visit represents a visit that is not as per Schedule of Assessments and is required for an adverse event or for potential relapse assessment. All indicated assessments are NOT performed at each unscheduled visit. Assessments would be symptom driven (e.g., only perform PML neurologic examination if patient reports symptoms suspected to indicate PML). pMCS to be conducted if patient experiences disease worsening and if stool frequency and rectal bleeding are available in the e-diary. Assessments corresponding to items noted in this column should be recorded on the eCRF.

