- ^l Each patient entered into the study will have one paired colonic biopsy sample (2 samples) taken during flexible sigmoidoscopy/colonoscopy procedure at Week 108 and placed in formalin and then paraffin embedded. The paired biopsy sample should be taken from the worst affected segment visualized (up to and including the descending colon). For patients without inflammation on endoscopy, the paired biopsy sample should be taken from the worst affected area visualized in the last endoscopy (up to and including the descending colon). In RCR consenting patients only, any residual or not entirely consumed colonic biopsy sample obtained at Week 108 will be stored in the RCR and will be destroyed no later than 15 years after the date of final closure of the associated clinical database. Original biopsy location and endoscopic depth should be clearly indicated.

Appendix 1

Open-Label Extension (Part 1, OLE) Schedule of Assessments (cont.)

- ^m For women of childbearing potential, including those who have had a tubal ligation. Perform a urine pregnancy test; if the urine pregnancy test result is positive, perform a confirmatory serum pregnancy test. Pregnancy test will be carried out at home once the patient starts etrolizumab administration at home. Patient is to report the pregnancy test result via e-diary. Patients must be reminded throughout the study that in case of a positive pregnancy test, they should stop self-administration of study drug and call the site immediately. Do not administer etrolizumab unless the serum pregnancy test result is negative.
- ⁿ Includes hemoglobin, hematocrit, platelet count, RBC count, mean corpuscular hemoglobin, mean corpuscular volume, mean corpuscular hemoglobin concentration, red cell distribution width, WBC count, and differential.
- ^o Includes sodium, potassium, chloride, bicarbonate, glucose, blood urea nitrogen, creatinine, calcium, phosphorus, magnesium, total and direct bilirubin, total protein, albumin, aspartate aminotransferase, alanine aminotransferase, lactate dehydrogenase, alkaline phosphatase, creatine phosphokinase, and uric acid.
- ^p Only enrolled patients who were hepatitis B core antibody positive in the Phase III study of origin should have hepatitis B DNA measured at these timepoints.

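### No age limit on a carried-over Week 0 pregnancy test: for GA28948/GA28949 Week 10 exits the first OLE dose can rest on a test 14 to 28 days old, if the parent study did not test after Week 10

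*Protocol*

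**What the plan says.** Section 4.4.1 of the protocol uses the procedures and laboratory results from the parent study's last visit as the data for the first OLE visit. ATA samples are the one exception, to be redrawn if Week 0 falls more than 7 days after that visit. For everything else the rule is: "Only if any procedure and assessment was missed at the time of the final visit, it should be performed for the first visit". Appendix 1 footnote b, attached to the Week 0 column, says that items already collected "do not need to be repeated, with the exception of ATAs, which must be collected at Week 0", under the same 7-day condition. The pregnancy test is marked in that column.

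On testing in general, Section 4.4.1.4 says: "All women of childbearing potential (including those who have had a tubal ligation) will have a urine pregnancy test performed at monthly intervals". It also says: "Urine pregnancy tests will be performed at specified subsequent visits", or at home. Appendix 4 likewise places the pre-dose urine test at subsequent visits. Appendix 1 footnote m, after describing what to do about a positive urine test, adds: "Do not administer etrolizumab unless the serum pregnancy test result is negative".

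On timing, Section 4.1.1 deals with GA28948/GA28949 patients who leave at Week 10 because they are not in remission or needed rescue medication. They may not be dosed "until 2 weeks after the Week 10 timepoint in the Phase III controlled study to allow for adalimumab washout". It then sets the upper limit: "The first dose of etrolizumab given to these patients entering Study GA28951 should not exceed 4 weeks following the Week 10 timepoint". Section 4.1.2 excludes anyone who "did not complete the required washout period for an active comparator in Studies GA28948, GA28949, and GA29103".

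**The concern.** The carry-over rule recognises that a result can be too old to use, but sets a limit only for ATA. The pregnancy test has none, although pregnancy excludes a patient from Part 1 (Section 4.1.2) and requires study drug to be stopped (Section 4.5.1.1). Section 4.2 expects that a substantial share of patients may be having their first etrolizumab exposure at entry, so for them the dose in question is the first one ever.

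A site that follows the written rule can give that dose on a test several weeks old. Later OLE doses are better covered, because Appendix 4 calls for a urine test before drug and withholds drug that day if it is positive. What is at stake is avoidable exposure in an unrecognised early pregnancy. No endpoint, estimate or analysis set is affected.

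**Working it through.** The plan states no figure for the age of a carried-over test, so there is none to reproduce. The check is calendar arithmetic.

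**Inputs**

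- Earliest first OLE dose for Week 10 exits: 2 weeks after Week 10, i.e. parent Week 12 (Section 4.1.1).
- Latest first OLE dose: 4 weeks after Week 10, i.e. parent Week 14 (Section 4.1.1). Table 1 footnote a agrees: 2 weeks plus a maximum delay of 2 weeks.
- Next scheduled pregnancy test after Week 0: OLE Week 4, i.e. 28 days after Day 1, with a window of ±3 days (Appendix 1).
- Day of the last parent-study test: not in the documents. Week 10 and Week 12 are both tried, the latter because a washout has to be completed.

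**Formulas**

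- Age at first dose = (parent week of first dose − parent week of last test) × 7.
- Interval between tests = age at first dose + 28 days.
- Excess = interval − 28 days, the OLE test spacing.

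**Last parent test at Week 10**

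- Age: (12 − 10) × 7 = 14 days, to (14 − 10) × 7 = 28 days.
- Interval: 14 + 28 = 42 days, to 28 + 28 = 56 days.
- With the visit window: 42 − 3 = 39 to 56 + 3 = 59 days.
- Excess: 42 − 28 = 14 to 56 − 28 = 28 days.

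**Last parent test at Week 12**

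- Age: (12 − 12) × 7 = 0 days, to (14 − 12) × 7 = 14 days.
- Interval: 0 + 28 = 28 days, to 14 + 28 = 42 days.
- With the visit window: 28 − 3 = 25 to 42 + 3 = 45 days.
- Excess: 0 to 14 days.

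| Case | Age at first dose (days) | Interval to OLE Week 4 test (days) | With ±3-day window (days) |
|---|---|---|---|
| Last parent test at Week 10 | 14–28 | 42–56 | 39–59 |
| Last parent test at Week 12 | 0–14 | 28–42 | 25–45 |
| Test on OLE Day 1 | 0 | 28 | 25–31 |

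If the test was missed at the parent final visit, Section 4.4.1 already calls for one at Week 0. The last row then applies and there is no gap.

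**Does other text require a fresh Week 0 test?**

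- Monthly testing (Section 4.4.1.4): a test 14 to 28 days old at first dose is within a month. The 42 to 56 days between tests is not, although the rule does not expressly cover an interval that spans two studies.
- Pre-dose testing (Section 4.4.1.4 and Appendix 4): both speak of subsequent visits, which does not clearly include Week 0.
- Footnote m: the serum condition follows the instructions for a positive urine result. Taken as a stand-alone rule it would demand a serum test before every dose, which contradicts the urine-first scheme.
- Eligibility review before the first dose (Section 4.4.3.1): it names no test.

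None of these closes the gap.

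**The case against.** The strongest objection is that the headline figure depends on documents not available here. The carried-over result comes from the parent study's final visit, and nothing in this protocol says outright that this is the Week 10 visit for these patients. If the final visit or last test falls at the end of the adalimumab washout, the age is 0 to 14 days. This stands as a limit on the size, and is why both cases are given. Section 4.1.1 does describe these patients as exiting at Week 10, so the longer case is plausible.

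A second objection is that Section 4.4.1 is about data use: it says which results populate the analysis data sets and does not authorise dosing on an old test. The next section, 4.4.1.1, calls for a partial physical examination on Day 1, so specific sections can override the general carry-over. But "Only if any procedure and assessment was missed at the time of the final visit, it should be performed for the first visit" governs what is performed at the visit, and so does footnote b. The physical-examination text also shows that the protocol can name a Day 1 procedure when it wants one, and it does not do so for the pregnancy test. It is fair that footnote b permits omission and does not forbid a test; the wording that leans against one is in Section 4.4.1.

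Third, the Week 0 box is ticked, Appendix 1 places assessments before dosing, and the word subsequent in Appendix 4 might mean subsequent to the parent study. That reading is possible but not clear, and footnote b's express waiver works against it.

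Finally, the consequence is small. Contraception is an entry condition, eligibility is reviewed before dosing, Section 1.2 reports no adverse events in embryo-fetal studies, and SAP Section 4.1.1 records that the sponsor terminated Part 1 on 15 February 2022. All of this stands. It keeps the severity low and means a change can no longer help patients entering this study.

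**Conclusion.** The concern holds. As written, the carry-over rule allows a first OLE dose without a current pregnancy test, and no other text clearly prevents it.

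For GA28948/GA28949 Week 10 exits, the test can be 14 to 28 days old at first dose, with 42 to 56 days between tests. That assumes a test at the Week 10 visit and none later in the parent study. With a Week 12 parent test the figures are 0 to 14 and 28 to 42 days. Confidence is medium because the parent schedule is unknown.

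This is an optional, low-severity improvement to patient safety with no effect on any analysis. After the termination of Part 1, its practical value lies mainly in any reuse of this wording in other rollover protocols.

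**What to change.** Add the pregnancy test to the exceptions in Section 4.4.1 and in Appendix 1 footnote b: every woman of childbearing potential has a urine pregnancy test at Week 0 (Day 1) before the first OLE dose, unless the parent study's final visit is on the same day. This brings the age at first dose to 0 days and the interval to the next test to 28 days (25 to 31 with the window).

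A weaker alternative is to extend the existing 7-day ATA limit to the pregnancy test. With the final visit at Week 10, the minimum gap of 14 days exceeds 7, so every such patient would be retested, and no carried-over result on any route could be more than 7 days old.

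The cost of the main proposal is two wording changes and one urine test at an in-clinic visit that already takes place and where the test is already ticked.
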